#### **3.5. Pharmacokinetic Analysis Set (PK)**

The population pharmacokinetic analysis set will include all patients in the pharmacokinetic subset who had at least 1 pharmacokinetic plasma sample analyzed for TV-45070.

## **4. GENERAL ISSUES FOR DATA ANALYSIS**

### **4.1. General**

Descriptive statistics for continuous variables include n, mean, standard deviation (SD), standard error of the mean (SE), median, minimum, and maximum. If inferential statistics are computed, it will also include least square mean and standard error of the least square mean, 95% confidence interval, and p-value, unless otherwise specified. Descriptive statistics for categorical variables include patient counts and percentages.

Summaries of potentially clinically significant abnormal values will include all postbaseline values (including scheduled, unscheduled, and early termination visits).

The last visit for efficacy and safety analyses and summaries is the last observed postbaseline data up to Week 4 visit.

### **4.2. Specification of Baseline Values**

For efficacy variables based on the weekly average of the daily average NRS scores, baseline is defined as the weekly average over the 7 days before randomization (day -7 to day -1). For other efficacy variables the baseline value is the last non-missing assessment on or before the first dose date if no assessment time is available. Otherwise, the baseline value is defined as the last non-missing assessment before the first dose of study medication.

The baseline value for safety variables (i.e., clinical laboratory, vital signs, ECG, and physical examination) is defined as the last non-missing assessment on or before the first dose date if no assessment time is available. Otherwise, the baseline value is defined as the last non-missing assessment before the first dose of study medication.

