### **4.4. Handling Withdrawals and Missing Data**

Missing onset/stop dates of AEs and prior/concomitant medications will not be imputed, and a conservative approach will be taken when assigning treatment-emergent AEs or concomitant medications.

The daily average NRS score is the average of the 2 NRS scores (recorded in the morning and evening). At least 1 of the 2 NRS scores must be non-missing or the daily average will be considered missing. The weekly average NRS score is the average of the daily average over 7 days.

For NePIQoL and NPSI questionnaires that include multiple items/tests, the measurement value at each timepoint is the sum of responses of all items/tests. If the entire questionnaire is not done at a scheduled time point, it will be considered missing and won't be imputed unless otherwise specified. Missing responses for individual items/tests will be imputed if up to 10% of the total items/tests for that scale are missing (up to 4 missing responses for NePIQoL, and 1 missing

response for NPSI). The imputed total is equal to the number of items in the scale times the sum of the non-missing responses divided by the number of non-missing items. If more than 10% of the responses are missing, then the total will be considered missing.

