### 6.3. Secondary Efficacy Variables and Analysis

#### 6.3.1. Variable Definition

- Weekly average of the average pain score recorded in the evening.
- Weekly average of the average pain score recorded in the morning.
- Weekly average of the worst pain score recorded in the evening (worst pain is defined as the patient-reported worst pain intensity over the prior 24 hours).
- $\geq 30\%$  improvement from baseline in the weekly average of the daily average NRS scores, where improvement from baseline is defined as  $100*(\text{weekly average of the daily average NRS scores at week 4} - \text{baseline weekly average of daily average NRS scores}) / \text{baseline weekly average of daily average NRS scores}$ .
- $\geq 50\%$  improvement from baseline in the weekly average of the daily average NRS scores, where improvement from baseline is defined as  $100*(\text{weekly average of the daily average NRS scores at week 4} - \text{baseline weekly average of daily average NRS scores}) / \text{baseline weekly average of daily average NRS scores}$ .
- NPSI is a patient-reported questionnaire to evaluate the severity of different symptoms of neuropathic pain. The questionnaire contains 10 descriptors and 2 temporal items. Descriptors are scored from 0 to 10, where 0 represents no pain and 10 represents worst pain imaginable. The total score is the sum of the scores of the 10 descriptors (Bouhassira, Attal, Fermanian, Alchaar, et al, 2004). The total score ranges from 0 to 100, where higher scores represent worse pain. If the score for one question is missing the total score will be computed as 10 times sum of scores of 9 descriptors divided by 9. If more than one question is missing then the total score will

be missing. The 2 temporal items will be summarized as continuous variable using descriptive statistics.

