### 6.3.2. Secondary Efficacy Analysis

The above secondary efficacy variables will be analyzed in the similar way as the primary analysis for the primary efficacy variable.

- Change from baseline to weeks 1, 2, 3 and 4 in the weekly average of the average pain score recorded in the evening
- Change from baseline to weeks 1, 2, 3 and 4 in the weekly average of the average pain score recorded in the morning

- Change from baseline to weeks 1, 2, 3 and 4 in the weekly average of the worst pain score recorded in the evening (worst pain is defined as the patient-reported worst pain intensity over the prior 24 hours)
- Change from baseline (randomization visit) to weeks 2 and 4 in the NPSI score
- Change from baseline (randomization visit) in DSIS scores at weeks 2 and 4
- Change from baseline (randomization visit) to weeks 2 and 4 in maximal intensity of patients' brush-evoked allodynia, as measured on the 11-point NRS
- Change from baseline (randomization visit) to weeks 2 and 4 in maximal intensity of patients' punctate-evoked hyperalgesia using a Medipin, as measured on the 11-point NRS

In addition, the following analyses will be done:

[figure not shown]
- Percentage of patients with  $\geq 30\%$  improvement and  $\geq 50\%$  improvement from baseline in the weekly average of the daily average NRS scores at week 4 will be analyzed using logistic regression model with pooled study center, treatment as fixed factors and baseline NRS scores as covariate.
- Time to reach  $\geq 30\%$  sustained improvement from baseline in the weekly average of the daily average NRS scores will be summarized using Kaplan-Meier method.
- Patients' global assessment of treatment, as measured by PGIC scores, at weeks 2 and 4 will be analyzed using a MMRM model similar to the primary efficacy variable with pooled study center, week, treatment, and treatment by week interaction as fixed factors and patient as a random factor. The unstructured covariance matrix for repeated observations within patients will be used.
- Change from baseline (randomization visit) to week 4 in the NePIQoL score will be analyzed using an analysis of covariance (ANCOVA) model with pooled study center, treatment as fixed factors and baseline value as covariate. The missing week 4 values will be imputed using last observation carried forward (LOCF) method.

[figure not shown]
SAS code for ANCOVA model

[figure not shown]
```
Proc mixed data=datain order=data;
  Class center treatment;

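### As worded, SAP 4.2 gives the evening, morning and worst-pain weekly averages a one-entry baseline instead of the mean over days -7 to -1

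*SAP*

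**What the plan says.** SAP 4.2 has two baseline rules for efficacy.

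- The first: "For efficacy variables based on the weekly average of the daily average NRS scores, baseline is defined as the weekly average over the 7 days", namely days -7 to -1.
- The second: "For other efficacy variables the baseline value is the last non-missing assessment on or before the first dose date". That form is for entries with no recorded time; where a time is available, it is the last non-missing assessment before the first dose.

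SAP 4.4 and 6.2.1 define the daily average as the mean of a morning and an evening score. SAP 6.3.1 then lists three further diary variables as separate items: "Weekly average of the average pain score recorded in the evening", then "Weekly average of the average pain score recorded in the morning" and "Weekly average of the worst pain score recorded in the evening". It gives none of them a baseline of its own. SAP 6.3.2 analyses each as a change, for example "Change from baseline to weeks 1, 2, 3 and 4 in the weekly average of the average pain score recorded in the evening", using the primary model, in which baseline is also a covariate.

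**The concern.** None of the three variables is a daily average. Worst pain is the clearest case: it is a separate diary item with a 24-hour recall and never enters the daily average. All three therefore fall under the second rule of 4.2. For a diary item, the last assessment before the first dose is one entry: the pre-dose day 1 morning score for morning pain, and the day -1 evening score for evening and worst pain.

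The weekly post-baseline value averages up to seven entries, so the change score would set a mean against one noisier reading, and that same reading would serve as the covariate. The three endpoints would lose precision. They would also no longer line up with the primary endpoint, which comes from the same diary but uses a 7-day baseline. A programmer who follows 4.2 and one who follows the apparent intent would produce different datasets.

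**Working it through.** **The plan's own figure.** SAP 2.3 assumes a difference of 1.0, SD 2.35, 80% power and two-sided 5%. The normal approximation gives n = 2 × (1.960 + 0.842)² × 2.35² / 1.0² = 86.7, so 87 per arm. The t test needs 88 (power 80.2%), and 88 / 0.80 = 110 randomized per arm. The stated 88 and 110 reproduce. They are set on the primary endpoint and do not depend on this point.

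**Which rule applies.**

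- Daily average NRS, the 30% and 50% responder endpoints, and time to sustained 30% improvement: all rest on the weekly average of the daily average, so the first rule applies.
- Evening, morning and worst-pain weekly averages: not based on the daily average, so the second rule applies as written.
- NPSI, NePIQoL, DSIS, allodynia and hyperalgesia: second rule, as is appropriate for visit-based measures.

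**Size.** The documents give neither of the two quantities needed, so both are assumed:

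- ICC, the correlation between single daily entries within a week: 0.5 to 0.9.
- r, the correlation between a 7-day baseline mean and the week 4 mean: 0.4 to 0.7.

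Daily scores are taken to vary independently around a stable patient mean. The week 4 mean and the 7-day baseline mean are given equal SDs, and a single-covariate model stands in for the week 4 contrast of the MMRM.

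- Reliability of a 7-day mean: rel7 = 7·ICC / (1 + 6·ICC)
- Baseline variance, one entry relative to the 7-day mean: V = 1 / (ICC + (1 − ICC)/7)
- Correlation of one entry with week 4: r1 = r·√(ICC / rel7)
- Ratio of adjusted standard errors: √[(1 − r1²) / (1 − r²)]
- Ratio of raw-change SDs: √[(1 + V − 2r) / (2 − 2r)]

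Mid-case, ICC 0.7 and r 0.6:

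- rel7 = 4.9 / 5.2 = 0.942
- V = 1 / (0.7 + 0.3/7) = 1.346
- r1 = 0.6 × √(0.7 / 0.942) = 0.517
- Adjusted standard error ratio = √(0.733 / 0.640) = 1.07
- Raw-change SD ratio = √(1.146 / 0.8) = 1.20

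| Case | ICC | r | Baseline variance | Adjusted SE | Raw-change SD |
|---|---|---|---|---|---|
| Low | 0.9 | 0.4 | ×1.09 | ×1.01 | ×1.04 |
| Mid | 0.7 | 0.6 | ×1.35 | ×1.07 | ×1.20 |
| High | 0.5 | 0.7 | ×1.75 | ×1.19 | ×1.50 |

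The adjusted model suffers less than the raw change because the covariate absorbs part of the baseline noise. The raw-change column still matters, since SAP 6.3.2 also plans descriptive summaries of change.

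**The case against.** The best reply is that a 7-day mean was plainly meant.

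- SAP 2.1 describes a baseline pain score averaged over days -7 to -1, and protocol 3.1 says the same.
- SAP 6.2.1 computes baseline from those days.
- The endpoint lists in SAP 2.2.2 and 6.3.2 name the randomization visit as baseline for the visit-based measures but not for these three.
- SAP 6.3.2 says the three are analysed like the primary.
- SAP 10 records no change to the diary baseline.
- The last assessment of a variable that is itself a weekly average could be read as the last pre-dose weekly average.

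As evidence of intent, this stands. It does not repair the rule. SAP 6.2.1 sits inside the primary variable's definition. SAP 2.1 speaks of average pain and does not mention worst pain. The instruction in 6.3.2 also covers NPSI, DSIS, allodynia and hyperalgesia, so it cannot carry a 7-day baseline with it. The protocol cannot override 4.2, because the SAP's preface gives the SAP precedence where the two differ. And if the last assessment of a weekly average were already the weekly mean, the first rule of 4.2 would have been unnecessary.

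A reader might go further and infer that the date-only clause lets the day 1 evening score, recorded after the first dose, become the baseline. That requires diary entries with no usable time. The diary collects morning and evening scores as separate entries in set windows, and nothing in the documents suggests that the times or session labels are missing. The documents do not support that reading.

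**Conclusion.** The point holds as a defect of wording: followed literally, SAP 4.2 compares a 7-day mean with one diary entry for three secondary endpoints. The documents do not show that a single-entry baseline was intended; a drafting error is the likelier explanation.

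A reader might also infer a biased treatment comparison or a threat to the primary result. Neither follows. A pre-dose entry is noisy in the same way in every arm, so the baseline-adjusted randomized comparison is not biased. The primary, responder and time-to-sustained-30% endpoints keep the 7-day baseline explicitly.

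The loss is in precision and in coherence with the primary endpoint. The adjusted standard error is about 1% to 19% larger, with 7% in the mid-case, and the raw-change SD is about 4% to 50% larger. These ranges rest entirely on the assumed ICC and r and on independent day-to-day noise; serial correlation between days would change them. At the low end the effect is negligible. The correction is worth making because it is nearly free and removes a choice that would otherwise fall to the programmer.

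**What to change.** Before unblinding, replace the first sentence of SAP 4.2 with text to this effect:

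*For all weekly averages of eDiary NRS scores (daily average, evening, morning and evening worst pain), baseline is the mean of the available scores for days -7 to -1, using the windows of Section 6.2.1. Morning scores take the same next-morning shift, so the last one is the pre-dose morning score of day 1.*

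The shift keeps the morning baseline consistent with the daily average, which already pairs each evening with the following morning. Keep the last-assessment rule for NPSI, NePIQoL, DSIS, allodynia and hyperalgesia.

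The cost is a one-sentence replacement in the SAP. No new data are needed: average and worst pain are both recorded in the eDiary from the baseline visit, and inclusion criterion c already requires pain records on at least 5 of 7 mornings and 5 of 7 evenings before randomization. The sample size does not change.

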### **4.3. Multiple Comparisons and Multiplicity**

This is a Phase 2 study, and there is no plan to adjust for multiplicity.

### **4.4. Handling Withdrawals and Missing Data**

Missing onset/stop dates of AEs and prior/concomitant medications will not be imputed, and a conservative approach will be taken when assigning treatment-emergent AEs or concomitant medications.

The daily average NRS score is the average of the 2 NRS scores (recorded in the morning and evening). At least 1 of the 2 NRS scores must be non-missing or the daily average will be considered missing. The weekly average NRS score is the average of the daily average over 7 days.

For NePIQoL and NPSI questionnaires that include multiple items/tests, the measurement value at each timepoint is the sum of responses of all items/tests. If the entire questionnaire is not done at a scheduled time point, it will be considered missing and won't be imputed unless otherwise specified. Missing responses for individual items/tests will be imputed if up to 10% of the total items/tests for that scale are missing (up to 4 missing responses for NePIQoL, and 1 missing

response for NPSI). The imputed total is equal to the number of items in the scale times the sum of the non-missing responses divided by the number of non-missing items. If more than 10% of the responses are missing, then the total will be considered missing.

#### **4.5. Study Days and Visit Windows**

For both safety and efficacy by-visit summaries, the assessments at the scheduled visits will be summarized in the tables while all of the assessments including unscheduled visits will be listed. For patients who withdraw from the study, data at the early termination visit will be included in the last visit summaries. The last visit is defined as last observed postbaseline data up to Week 4 visit.

If there are multiple assessments at a scheduled postbaseline visit then the last non-missing value at that visit will be used for the by visit summary.

Study days will be numbered relative to the first day of study drug administration. The start of treatment (day 1) is defined as the date on which a patient applies the first dose of study drug, as recorded on the study drug diary. Days will be numbered relative to study start (ie, ..., -2, -1, 1, 2, ...; with day 1 being the start of study drug and day -1 being the day before the start of study drug).

#### **4.6. Center**

The trial will be conducted in approximately 55 study centers in the United States. In order to include center into the model, centers will need to be combined to create approximately 15 big centers. Centers may be pooled according to the number of patients enrolled at each site by keeping the largest sites intact and pooling the remainder of the larger sites with smaller sites to form pooled sites. A final plan for pooling will be made and documented in Statistical Data Review meeting minutes prior to unblinding. The pooled centers will be used in the efficacy analyses as appropriate.

## **5. STUDY POPULATION**

### **5.1. General**

All randomized patients will be used for all study population summaries unless otherwise noted. Summaries will be presented by treatment group and for all patients (overall) unless otherwise noted.

### **5.2. Patient Disposition**

Data from patients screened, patients screened but not randomized and reason not randomized will be summarized only for the overall group using patient counts. Patients randomized, patients randomized but not treated (and reason), patients in the ITT, safety, FAS, and PP populations, patients who complete double-blind treatment, patients who withdraw from double-blind treatment, patients who complete the study, and patients who withdraw from the study will be summarized using descriptive statistics. Data from patients who withdraw from the double-blind treatment and from the study will also be summarized by reason for withdrawal using descriptive statistics. This summary will include all patients screened into the study. The denominator for calculating percentages will be the number of randomized patients.

### **5.3. Demographics and Baseline Characteristics**

Patient demographic and baseline characteristics, including medical history, prior medications, and ECG findings will be examined to assess the comparability of the treatment groups and will be summarized using descriptive statistics by treatment group and total. For continuous variables, descriptive statistics (number [n], mean, standard deviation (SD), standard error (SE), median, minimum, and maximum) will be provided. For categorical variables, patient counts and percentages will be provided. Categories for missing data will be presented if necessary.

### **5.4. Medical History**

Patients with a medical history assessment will be summarized using descriptive statistics.

### **5.5. Prior Medications**

All prior medications will be coded using the World Health Organization dictionary of medical codes (WHO Drug Version March 2014 enhanced B2 format). The incidence of prior medications will be summarized using descriptive statistics by therapeutic class (ATC level 2) and preferred term. Patients are counted only once in each therapeutic class category, and only once in each preferred term category. Prior medications will include all medications taken prior to the first day of study drug.

### **5.6. Electrocardiography**

Electrocardiogram findings (normal, abnormal, and missing) at baseline will be summarized using descriptive statistics.

## **5.7. Protocol Violations**

Patients with at least 1 protocol violation for each category will be summarized using descriptive statistics. Patients with at least 1 major protocol violation for each category will also be summarized using descriptive statistics. Descriptions will be reviewed and rescue medication overuse will be summarized as a separate category.

## **5.8. Childbearing Potential**

For female patients, information related to childbearing potential, contraception, and menopause will be collected at screening visit. The number of patients in each category will be reported by treatment group for randomized patients.

## 6. EFFICACY ANALYSIS

### 6.1. General

The FAS will be used as the primary analysis for all efficacy analyses. The PP population will be supportive for efficacy analyses. All statistical testing will be carried out using 2-tailed tests at the 5% level of significance. Summaries will be presented by treatment group as randomized/assigned unless specified otherwise.

### 6.2. Primary Efficacy Variable and Analysis

#### 6.2.1. Variable Definition

The NRS is a widely-used, standard one-dimensional scale from 0 to 10 for patient self-reporting of pain. The daily average NRS scores are the average of the 2 NRS scores (recorded in the morning and in the evening) of average pain, defined as the patient-reported average pain intensity over the prior 12 hours. At least 1 of the 2 daily scores must be recorded (non-missing) or the daily average will be considered missing. The daily average NRS scores are the average of evening NRS score on day x and morning NRS score on day x+1. For example, the daily average NRS score on day 1 (day of first study medication) is the average of evening NRS score on day 1 and morning NRS score on day 2. Similarly the daily average NRS score on day 28 is the average of evening NRS score on day 28 and morning NRS score on day 29. The weekly average of the daily average is computed over the 7 days. Baseline is computed using days -7 to -1, week 1 using days 1 to 7, week 2 using days 8 to 14, week 3 using days 15 to 21 and week 4 using days 22 to 28.

#### 6.2.2. Primary Analysis

The primary efficacy variable for this study is the change from baseline to week 4 in the weekly average of the daily average NRS pain scores. This variable will be analyzed using a Mixed Model Repeated Measures (MMRM) model with change from baseline in the weekly average of the daily average NRS scores at weeks 1, 2, 3 and 4 as the dependent variable; week, pooled study center, treatment, and treatment by visit interaction as fixed factors, baseline weekly average of the daily average NRS scores as covariate; and patient as a random effect. The unstructured covariance matrix for repeated observations within patients will be used. If the model does not converge, the maximum-likelihood (ML) estimation method will be used instead of the default restricted ML (REML) method. If the model still does not converge, then simpler covariance structures with less parameters will be used in the following order until the model does converge: heterogeneous autoregressive (1) (ARH[1]); heterogeneous compound symmetry (CSH); autoregressive (1) (AR[1]); and compound symmetry (CS). The primary treatment comparison will be conducted at week 4 in this model.

The least square (LS) means and standard error of each treatment group, LS means differences including standard error, 95% confident interval (CI) and p-values, between each active group and the placebo group for the change from baseline to weeks 1, 2, 3 and 4 in the weekly average of the daily average NRS pain scores will be presented in the tables.

SAS code for primary endpoint:

```

Proc mixed data=datain;
Class treatment week patient;
Model change=base treatment center week treatment*week/ddfm=kr;
Repeated week/sub=patient type=un;
Lsmean treatment*week/pdiff cl ;
*** treatment order in the data will be placebo, 4%, 8%*****;

Estimate '4% vs. Placebo at week 4' treatment -1 1 0 treatment*week 0 0 0 -1
0 0 0 1 0 0 0 0/ cl;
Estimate '8% vs. Placebo at week 4' treatment -1 0 1 treatment*week 0 0 0 -1
0 0 0 0 0 0 1/cl;

Run;

```

A descriptive summary of the weekly average of the daily average NRS pain scores at baseline, weeks 1, 2, 3 and 4, as well as the change from baseline will be provided by treatment group.

